Does your study meet the definition of a clinical trial and recin accordance with ICMJE? ICMJE definition of clinical trial: Any research study that passigns human participants or groups of humans to one or minterventions to evaluate the effects on health outcomes. Herinterventions include any intervention used to modify a biomelated outcome (for example, drugs, surgical procedures, detreatments, dietary interventions, and process-of-care change outcomes include any biomedical or health-related measures patients or participants, including pharmacokinetic measures events. Purely observational studies (those in which the assis medical intervention is not at the discretion of the investigat require registration. Refer to the following websites for guidance: ICMJE Clinical Trials Registration: http://www.icmjicmje/faqs/clinical-trials-registration/ Note: If your study meets the requirement for registration submit the National Clinical Trial (NCT) Identifier # to the IRB approval. NCT #:pending	prospectively nore health-related alth-related medical or health-revices, behavioral es). Health is obtained in its and adverse gnment of the for) will not its end, you must the IRB prior to
YES NO NIH Requirements	

×	Does your study meet the definition of an applicable clinical trial and require registration AND results submission in accordance with NIH?		
	As of January 18, 2017, NIH is requiring that clinical trials be registered at ClinicalTrials.gov. Confirm whether this study meets the registration requirements for clinical trial registration in accordance with the definition of a clinical trial as defined by NIH. See definition below.		
	Clinical Trial: A research study in which one or more human subjects are prospectively assigned to one or more interventions (which may include placebo or other control) to evaluate the effects of those intervention on health-related biomedical or behavioral outcomes". This definition encompasses phase 1 trials of FDA-regulated drug and biological products, small feasibility studies of FDA-regulated device products, and studies of any intervention not regulated by the FDA, e.g. behavioral interventions.		
	Of note, this requirement for registering and results reporting includes clinical trials beyond those already required by the FDA. The requirements are expanded to include to Phase I drug studies and NIH-funded clinical trials of social-behavioral interventions.		

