Parkinson disease (PD) is a chronic progressive health condition affecting older adults. Of particular concern is walking decline, which is a marker of emerging disability. Pathophysiologic changes in the basal ganglia result in a high expenditure of cognitive resources for once automatic movements, such as walking. Auditory cueing has been shown to compensate for impairments in the basal ganglia by harnessing the human capacity for rhythm perception through a mechanism called entrainment. Entrainment refers to the activation of motor-related centers of the brain in response to an external rhythmic stimulus. Direct sensorimotor connections between the auditory and motor system demonstrate the capacity for the auditory system to drive motor movement patterns. Music-based auditory cueing has demonstrated immediate and potent effects on walking, as reflected clinically by improvements in speed, stride length, and step frequency. Improvements

observed in the quality and thus, quantity, of walking make a music-based device a promising rehabilitation adjunct for persons with PD.

Study Objectives: The purpose of this study is to evaluate the effects of music, tailored to the participant's cadence, on adherence, quality of life, gait speed, functional mobility, and walking activity in individuals with Parkinson disease when used in the home and community environment.

Primary and Secondary Endpoints:

Primary Study Endpoints:

- Observed adherence to therapy schedule (feasibility)
- Mobility impact as assessed by PDQ-39 mobility dimension

Secondary Study Endpoints:

- Change in gait speed at baseline as compared to end of study participation (or earlier if the participant withdraws) as determined by the 10MWT
- Overall quality of life impact as assessed by PDQ-39
- Improvements in functional mobility as measured by the Five Times Sit to Stand test
- Change in amount (steps/day) and intensity (moderate intensity minutes; >100 steps/min) of walking activity as measured by the StepWatch Activity Monitor (SAM)

SECTION H: RESEARCH METHODS AND ACTIVITIES (Check all that apply)

	Collection of audio, video, digital, or image recordings
	Biological samples → Complete Biological Samples Form: http://www.bu.edu/researchsupport/compliance/human-subjects/ Examples: blood, hair, cheek swab, urine, tears, saliva, etc.

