- Walking Activity: Walking activity will be measured over a 4-day period prior to initiating the intervention and continuously measured for an additional 4 days upon intervention initiation (total of 8 days of data). The purpose of this sequence is to be able detect changes in walking activity that may occur with initiation of a structured walking program. For example, once the walking program is initiated, do participants appear to increase their walking activity compared to baseline (before initiating the walking program)? Is the increase in walking activity isolated to during the individual sessions, or is there an overall increase noted throughout the day? Walking activity will be measured using the StepWatch 4 Activity Monitor (SAM; Orthocare Innovations, Mountlake Terrace, Washington). The SAM is a self-contained, maintenance-free device that combines acceleration, position and timing information to count complete gait cycles (strides) of the user; it is the size of a pager, weighs 38g, and will be attached with self-adhesive straps above the lateral malleolus (where the shin meets the foot) of the participants' less impaired lower extremity. Participants will be instructed to wear the

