SAM for 8 consecutive days during all waking hours, expect when bathing, showering, or swimming. The physical therapist will fill out the SAM researcher form to appropriately document the SAM calibration process for each participant (see Appendix VII: Outcome Measures). Participants will be given instructions on how to don/doff the device and will be provided with a form to record times the SAM is removed over the 8day period (see Appendix VII: Outcome Measures). The SAM requires no maintenance by the user besides remembering to keep it on. The physical therapist will provide strategies to help the participant remember to put the SAM back on if they do take it off at any time (e.g., if the SAM is taken off at night, place it on a nightstand next to the bed so it is seen in the morning). Using the manufacturer's software, the SAM will be calibrated by a physical therapist to each participant's gait pattern based on height, typical walking speed, and leg motion. The validity and reliability of the SAM for capturing stride counts has been demonstrated in persons with various neurological disorders including PD (Shepard 1999, Coleman 1999, Macko 2002, Salarian 2004, Gaines 2005, Manns 2009, Speelman 2011). Collected data will be downloaded to a computerized tablet, with which manufacturer's software will convert stride counts to step counts and calculate daily step count values. No identifiable information is collected by the SAM. Participants will return the SAM to study personnel via a pre-labeled, addressed envelope to mail following the 8-day monitoring period. Participants will be contacted via phone within 24-48 hours following the evaluation session to ensure that they are comfortable with the device and to address any questions or concerns.

Training Procedures / Instruction to Participants:

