Overview: Following enrollment, participants will wear the SAM for a 4-day period prior to initiating the intervention (to collect baseline walking activity). After approximately 4 days, participants will initiate the walking program while continuing to wear the SAM for the first 4 days of the walking program. As the sensor for the music-based device is hooked onto the shoe and the SAM is worn on the lower leg (just above the ankle), both can be worn simultaneously on the same side of the body without interfering with a participant's walking and/or increasing the risk for trips/falls. Participants will be instructed to complete five home-based walking sessions per week (approximately 30-40 minutes in duration) for four weeks. Participants will be able to carry out their five (5) sessions a week on any days of the week according to their needs. Participant engagement in the walking program will be monitored remotely by the study team at the end of each week via a phone call. This phone call will last approximately 5-10 minutes (depending on whether the participant has questions/concerns and/or any medical/technical issues). During the evaluation visit, the research team will ask you at which time each week you would like to have this check-in call. If participants are unable to carry out the walking program 5-days per week, a study staff member will discuss the barriers to implementation (by phone) and suggest ways to optimize adherence to the program (e.g., setting a schedule). A study staff member will also inquire about adverse events during the weekly phone call and ensure that the participant is comfortable with the walking program.

Description of Walking Sessions: Using the music-based device, participants will conduct the walking sessions at their self-selected pace in a home/community environment that limits the amount of stops and/or pivot turns in order to optimize continuous walking. For the purposes of this study, home/community environment is considered any environment outside a professional healthcare facility. This includes but is not limited to the home, apartment building, independent living retirement homes, outdoor environments (tracks, parks, sidewalks), office environments and community/recreation centers. Participants will be asked to record in a study diary their schedule (dates and times) of walking, location, record of any falls they experience and any

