**Feasibility and Preliminary Effects of using a Music-based, Rhythm-modulating
Wearable Sensor System in the Community in Persons With Parkinson Disease**

Statistical Analysis Plan

NCT Number: NCT04891107

Date of Document: July 27, 2023

TEMPO Statistical Analysis Plan

Normality of distribution will be confirmed using Shapiro-Wilk test. Given the preliminary nature of this study, adjustments are not planned to account for multiple comparisons across outcomes.

Primary Outcomes:

- > Feasibility metrics will be measured descriptively
- > PDQ-39 mobility dimension will be assessed using paired t-tests ($\alpha = .05$) to compare baseline and post-intervention values

Secondary Outcomes:

> Change in disease severity (MDS-UPDRS III), walking endurance (6MWT), gait speed (10MWT), change in mobility (FTSTS) and overall quality of life (PDQ-39 total score) will be assessed using paired t-tests ($\alpha = .05$) to compare baseline and post-intervention values.

> Change in daily steps and moderate intensity minutes will be assessed using paired t-tests ($\alpha = .05$) to compare daily walking activity at baseline (days 1-4) to daily walking activity during the intervention (days 5-8).

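### The whole-day comparison of walking activity cannot show whether a rise is confined to the prescribed sessions or extends beyond them, a question the protocol poses as an example of what the monitoring is for

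*Protocol*

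**What the plan says.** Protocol Section L, Baseline Assessment, Walking Activity: the SAM is worn for four days before the programme starts and for its first four days, so that a change at programme start can be detected. Two example questions follow. The first is whether walking rises above baseline. The second is: "Is the increase in walking activity isolated to during the individual sessions, or is there an overall increase noted throughout the day"?

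Protocol Section G lists the secondary endpoint as "Change in amount (steps/day) and intensity (moderate intensity minutes; >100 steps/min) of walking activity", measured by the SAM. Section L says that the "manufacturer's software will convert stride counts to step counts and calculate daily step count values".

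SAP, Secondary Outcomes: "Change in daily steps and moderate intensity minutes will be assessed using paired t-tests", with alpha .05, "to compare daily walking activity at baseline (days 1-4) to daily walking activity during the intervention (days 5-8"). This is the SAP's only analysis of walking activity.

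On session timing, Section L (Description of Walking Sessions) says: "Participants will be asked to record in a study diary their schedule (dates and times) of walking, location". Section P says that the music device uploads data from each session. Neither document plans to remove session time or to analyse it separately.

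**The concern.** The two windows differ by design. Days 5-8 are the first four days of a programme of five sessions a week, with the SAM worn throughout; days 1-4 precede it. A whole-day total therefore mixes the steps of the assigned exercise with any change in the rest of the day. The same rise can appear whether other walking goes up, stays level or partly falls because sessions replace it.

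Moderate-intensity minutes behave the same way. The threshold is above 100 steps/min, and in the protocol's own example the music tempo moves from 100 to 105. For a participant near that cadence, the session itself can produce the minutes being counted.

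At stake is the interpretation. A significant steps/day result could be reported as participants becoming more active in daily life when it may show only that they did the sessions in the first days, which the adherence endpoint already measures.

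**Working it through.** The documents give no power, effect size or SD for this endpoint, so there is no planned figure to reproduce. The session inputs can be checked: 5 sessions × 30 min × 4 weeks = 600 min = 10 h, which agrees with the programme total in Section L.

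**Inputs**
- Session goal: 30 min of walking with music (Section L, Description of Walking Sessions).
- Cadence: 100 steps/min (Section L, Music-Based Device Training). This is an example, not a measured mean.
- Frequency: five sessions a week on any days (Section L, Overview). At most one per day is my assumption.
- n = 20 with complete SAM data; two-sided alpha .05 (the SAP does not state sidedness).
- SD of within-person change in steps/day: not given; 2,000 to 4,000 assumed.

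**Step 1: what the sessions add.** One session is 30 × 100 = 3,000 steps. With the first session on day 5 and the other four placed anywhere in the remaining six days of that week, there are 15 placements. They put 2, 3 or 4 sessions in days 5-8 in 3, 9 and 3 of the 15 cases (mean 3). The contribution to the daily mean is 3,000 × sessions / 4:
- 2 sessions: 1,500 steps/day and 15 walking min/day
- 3 sessions: 2,250 steps/day and 22.5 walking min/day
- 4 sessions: 3,000 steps/day and 30 walking min/day

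Those minutes count as moderate intensity only where cadence exceeds 100 steps/min, so 15 to 30 min/day is an upper range. Without fixing day 5, the mean is 4 × 5/7 = 2.86 sessions, or 2,143 steps/day. Cadences of 80 to 120 and walks of 20 to 30 min widen the range to 800 to 3,600 steps/day.

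**Step 2: chance that the planned test is significant on sessions alone.** Paired t-test, 19 df, critical value 2.093, noncentrality = shift / SD × √20.

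| Net shift (steps/day) | SD 2,000 | SD 3,000 | SD 4,000 |
|---|---|---|---|
| 800 | 0.397 | 0.205 | 0.136 |
| 1,125 (half of 2,250 offset elsewhere) | 0.665 | 0.357 | 0.223 |
| 1,500 | 0.889 | 0.565 | 0.357 |
| 2,250 | 0.997 | 0.889 | 0.665 |
| 3,000 | >0.99 | 0.989 | 0.889 |

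**Step 3: why the total cannot separate the two.** These three cases give the same whole-day change:
- sessions +2,143, other walking 0: total +2,143
- sessions +1,072, other walking +1,071: total +2,143
- sessions +3,000, other walking −857: total +2,143

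A larger sample would not help, because the split is not in the quantity tested. This step needs none of the assumed SDs.

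**The case against.** The strongest reply is that the SAP and the listed endpoint agree. Section G asks for change in steps/day and moderate-intensity minutes, and the SAP tests exactly that. The in-session question is introduced only as an example. Total activity is a legitimate target: the sessions are part of the programme's effect, and the total correctly nets out any substitution. The SAP itself makes no claim about walking outside sessions, and this is a single-group pilot of up to 20 people. All of this stands. A reader might infer that the planned test is invalid or that a listed endpoint goes unanalysed; the documents support neither.

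A reader might also infer that the data for the split are certainly in hand. The documents stop short of that. The diary records dates and times but not explicitly stop times. Section P mentions session data without time stamps and describes them as performance data, from which secondary outcomes can be extracted. Minute-level SAM output is a fair inference from a threshold in steps/min, but the text describes only daily counts.

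It is also tempting to make the out-of-session result the sole basis for conclusions about daily-life walking. That goes too far. Removing session minutes from days 5-8 alone shortens the observed time on those days only. Someone who moves a usual 3,000-step walk into a session would show −3,000 steps outside sessions and no change overall.

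Finally, Section L has the SAM worn for four days after the post-intervention visit, when no sessions are prescribed. The SAP does not analyse that window, and it would address carry-over after the programme, not the split during it.

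**Conclusion.** The point holds as a gap in supporting analysis. The planned tests answer whether total activity rises at programme start. They cannot answer whether the rise is confined to sessions, which the protocol gives as one of two example questions behind the 4 + 4 day sequence.

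At the protocol's example cadence and session goal, sessions alone add about 1,500 to 3,000 steps/day. A session-only shift of 2,250 is significant with probability about 0.67 to >0.99 for SDs of 4,000 down to 2,000. A reader might infer that a significant result is close to assured from sessions alone, but the figures do not go that far: the probability is 0.565 at 1,500 steps/day with SD 3,000, and 0.136 to 0.397 at 800 steps/day. Cadence, session length, complete data and the SDs are all illustrative. The conclusion that whole-day totals cannot separate the two sources depends on none of them.

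**What to change.** - Keep the whole-day tests, and label them in the SAP as total activity including prescribed sessions.
- Add a supporting paired comparison, days 1-4 against days 5-8, of out-of-session steps and out-of-session moderate-intensity minutes.
- Define session time to include warm-up and cool-down. Identify it from the diary and, if time-stamped, from the device session data, with a stated rule for when the sources disagree.
- Express the out-of-session measures per hour of monitored wear outside sessions, or account in another stated way for the time removed.
- Report in-session, out-of-session and whole-day changes together, so that a usual walk moved into a session is read as substitution.
- State that a rise in walking outside sessions will not be claimed from the whole-day result alone.

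First confirm that the SAM export is at minute level and that session start and stop times can be obtained. If so, the cost is SAP wording and extra processing, with no new data collection or participant burden. The main weakness is possible mismatch between the SAM clock and the diary or device times. If the times cannot be obtained, the SAP should say that the in-session question will not be addressed.

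### The two adjacent 4-day step-monitor windows usually hold different numbers of weekend days, and the paired t-test does not adjust for this

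*Protocol*

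**What the plan says.** Protocol Section L (Baseline Assessment, Walking Activity) sets the design: "Walking activity will be measured over a 4-day period prior to initiating the intervention and continuously measured for an additional 4 days". The monitor is worn without a gap between the two windows ("SAM for 8 consecutive days during all waking hours"). The stated purpose is to detect a change in walking when a structured program begins, including whether any increase is confined to the sessions or spread over the day.

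The overview of the remote walking program in the same section is looser on timing: "After approximately 4 days, participants will initiate the walking program while continuing to wear the SAM for the first 4 days of the walking program". It also leaves the session days to the participant: "Participants will be able to carry out their five (5) sessions a week on any days of the week according to their needs".

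The SAP (Secondary Outcomes) states: "Change in daily steps and moderate intensity minutes will be assessed using paired t-tests". The contrast is days 1-4 against days 5-8. No other comparison of monitor data is listed. I found nothing in either document that fixes the weekday of monitor day 1, requires weekend days in each window, or includes a day-of-week term.

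**The concern.** Two adjacent 4-day windows cover eight days, one more than a week, so they cannot contain the same weekdays. For most start days, the share of weekend days changes at the same moment as the program begins. If people walk more or less at weekends, that habit enters the within-person difference together with the program effect, and a t-test on window means cannot separate the two.

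The trial has one group and no control arm, so nothing else in the design removes a calendar effect. The outcomes at stake are the two secondary walking-activity endpoints. The primary endpoints, adherence and the PDQ-39 mobility dimension, are not affected.

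**Working it through.** **Inputs from the documents.** Two adjacent windows of 4 days (Protocol Section L; SAP Secondary Outcomes). Twenty participants (Protocol Sections J and L). The documents give no figure of their own to reproduce on this point.

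**Input assumed.** Weekend-weekday difference in daily steps, Δ = 500 to 1,500. This equals 10-30% of an assumed 5,000 weekday steps. Neither figure is in the documents, and the sign of Δ is unknown.

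**Step 1: count weekend days by weekday of monitor day 1.** Let d = weekend days in days 5-8 minus weekend days in days 1-4.

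| Day 1 | Days 1-4 | Days 5-8 | d |
|---|---|---|---|
| Mon | 0 | 2 | +2 |
| Tue | 0 | 2 | +2 |
| Wed | 1 | 1 | 0 |
| Thu | 2 | 0 | -2 |
| Fri | 2 | 0 | -2 |
| Sat | 2 | 1 | -1 |
| Sun | 1 | 2 | +1 |

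Six of the seven start days are unequal. Four of the five Monday-Friday start days are unequal by two days.

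**Step 2: shift in one participant's difference.** Shift = (d/4) × Δ. For d = ±2, this is 0.5 × 500 = 250 to 0.5 × 1,500 = 750 steps/day, in a direction set by the start day and the sign of Δ.

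**Step 3: group mean, starts spread at random over Monday-Friday.** The mean of d is (2 + 2 + 0 - 2 - 2)/5 = 0, so there is no bias in expectation. The SD of d is √[(4 + 4 + 0 + 4 + 4)/5] = √3.2 = 1.79 weekend days. Per participant, the added SD is (1.79/4) × 500 to 1,500 = 224 to 671 steps/day. For the mean of 20, the SD of d is 1.79/√20 = 0.40 weekend days, which gives (0.40/4) × 500 to 1,500 = 50 to 150 steps/day.

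**Step 4: group mean, an uneven pattern.** Suppose visits are spread evenly over Monday-Friday and wear begins the next day, so day 1 runs from Tuesday to Saturday. The mean of d is (2 + 0 - 2 - 2 - 1)/5 = -0.6, and the mean shift is (0.6/4) × 500 to 1,500 = 75 to 225 steps/day, opposite in sign to Δ.

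**Step 5: can the two effects be separated?** Yes. Every row of the table leaves at least two weekdays in each window, so a weekend term and a period term can both be estimated from the eight daily values.

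**The case against.** A reader might infer that the planned comparison is biased by 250-750 steps/day. The documents do not support that. The range is the shift for one participant with an unfavorable start day, and the SAP tests a group mean, in which opposite signs offset each other. Net bias needs uneven start days, and the documents say nothing about which days visits or wear begin.

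The size also depends wholly on an assumed weekend difference. If walking hardly varies over the week, the problem largely disappears. No size can be given for moderate intensity minutes, because there is no figure to work from.

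Set against a plausible signal, the group effect is modest. The Protocol's goal of 30 minutes per session, at its example cadence of 100 steps/minute, gives 3,000 steps. Five sessions a week give 3,000 × 5/7 ≈ 2,140 steps/day, if sessions add to usual walking (an assumption). The 50-150 steps/day of noise is then about 2-7% of the signal. These are secondary outcomes in a pilot that the SAP itself calls preliminary.

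All of this stands, and it limits the size of the point. It does not remove it: the count is exact, the plan has no safeguard, and the adjustment needs no new data.

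**Conclusion.** The point holds as a weakness in design and analysis that is cheap to repair. For the exact split in the SAP, the windows hold unequal numbers of weekend days for every day-1 weekday except Wednesday, and the paired t-test carries any weekend difference into the estimated change.

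On an assumed difference of 500-1,500 steps/day, the main consequence is lost precision: up to 250-750 steps/day in one person's change, and an SD of about 50-150 steps/day in the mean of 20 with random Monday-Friday starts. A directional bias is possible but not shown. It requires uneven starts, of which 75-225 steps/day is one example. The count is certain; the size is only as good as the assumed weekend difference.

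**What to change.** In the SAP, replace the t-test on window means with a mixed model on the eight daily values per participant. Include a participant effect, a period term (before versus from the actual program start) and a weekend-day term, and allow for correlation between consecutive days. Defining period by the actual start date also deals with the Protocol's approximate timing. Report the period effect and the distribution of start weekdays. The unadjusted paired t-test can be kept as a sensitivity analysis.

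The cost is wording. The Protocol already has the monitor software produce daily step counts, and no extra wear, visits or participants are needed. The model spends one extra parameter on the weekend effect and assumes that this effect is the same in both periods. That may not hold exactly when participants choose their session days, and should be stated as a limitation.

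Starting all wear on a Wednesday is not a substitute. It balances the windows only if every participant begins the program exactly on day 5, a Sunday. A program start one day later, on Monday, makes the first four program days Monday-Thursday: no weekend day, against one in days 1-4.

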steps/minute, once considered entrained, the tempo will increase to 105 steps/minute. This increase is very small and will most likely not be noticed by the participant. If the participant is unable to increase their cadence to match this tempo, the tempo is reduced back to baseline. The algorithm used to set the tempo is dynamic and adjusts to the cadence of the participant. If a participant feels that they cannot keep up with the faster cadence, they can continue walking at their comfortable pace. Participants will also be instructed to stop the intervention if they feel uncomfortable or anxious at any time. Following this training, it is expected that participants will be able to independently setup (including donning/doffing the device), perform and conclude a walking session independently. Participants will have access to Instructions for Use (IFU) that will detail all procedures required for proper operation of the system. However, participants will be encouraged to contact the research team if they have any additional questions, issues or concerns. Participants will be excluded from the study if unable to demonstrate how to use the device independently as determined by the physical therapist. Please note, participants will be provided with a pre-established username and password. No personally identifiable information will be recorded or stored in the device application.

Remote Walking Program Description (10 hours total over four weeks + concurrent use of SAM device over 4 walking days)

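### Do the SAP's fixed step-monitor windows (days 1-4 and 5-8) conflict with a walking program that starts after approximately four days?

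*Protocol*

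**What the plan says.** The SAP, under Secondary Outcomes, uses a paired t-test at the 5% level to compare "daily walking activity at baseline (days 1-4) to daily walking activity during the intervention (days 5-8"). The windows are numbered, and each is also named by the phase it represents.

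The protocol describes the same monitoring in Section L. Under Walking Activity, activity is recorded for four days before the intervention and then "continuously measured for an additional 4 days upon intervention initiation (total of 8 days of data"). The wearing instruction there is "SAM for 8 consecutive days during all waking hours". The Overview of the Remote Walking Program first states a four-day period before initiation with no qualifier, and then says: "After approximately 4 days, participants will initiate the walking program while continuing to wear the SAM for the first 4 days" of the program. The heading of that section has a third wording, "concurrent use of SAM device over 4 walking days".

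On sessions, the Overview says: "Participants will be able to carry out their five (5) sessions a week on any days of the week according to their needs". Participants record the dates and times of their walks in a diary (Section L, Description of Walking Sessions). Section G lists the outcome among the secondary endpoints: "Change in amount (steps/day) and intensity (moderate intensity minutes; >100 steps/min) of walking activity".

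**The concern.** One document counts days from an origin it does not define, and the other counts from an event it allows to move. If a participant starts on day 4, the SAP's baseline window contains a program day. If the start is on day 6, the intervention window contains a day before the program. Either way two kinds of day are mixed and a real change shrinks. Neither document says whether the fitting day is day 1, whether initiation means a scheduled date or the first home session, or what to do with a start on another day.

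The comparison has a stated purpose. Walking Activity explains that the sequence is meant to show what happens when the program begins, and asks: "Is the increase in walking activity isolated to during the individual sessions, or is there an overall increase noted throughout the day". Blurring the boundary between the phases blurs that answer. An analyst who chose where to cut after seeing the data could also move the result.

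**Working it through.** **1. The plan's own count.** Four days before initiation plus four days after gives 4 + 4 = 8, which is the total stated under Walking Activity and the length of the wearing instruction. Taking day 1 as the first wear day (the natural reading, though not stated), the program starts on day 5 and the windows are days 1-4 and 5-8. The SAP's numbers are the protocol's schedule written as day numbers.

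**2. The third wording.** Suppose the section heading meant four days with a session. Five sessions in seven days can be placed in 21 ways. The first four program days then hold 4, 3 or 2 sessions in 3, 12 and 6 of them. Four session days would therefore fit into days 5-8 in only 3 of 21 cases (14%), which does not sit with a fixed eight-day wear. The heading is best read as shorthand for the first four days of the program.

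**3. Off-schedule starts under literal windows.** Let the program start on day s, with the same effect on every program day. Share of contrast kept = (program days within 5-8 minus program days within 1-4) / 4.

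| Start day | Program days in 5-8 | Program days in 1-4 | Share kept |
|---|---|---|---|
| 3 | 4 | 2 | 50% |
| 4 | 4 | 1 | 75% |
| 5 | 4 | 0 | 100% |
| 6 | 3 | 0 | 75% |
| 7 | 2 | 0 | 50% |

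The documents do not say how many participants start off schedule. As assumed shares, 25% of participants one day off keeps 1 − 0.25 × 0.25 = 93.75% of the group contrast, and 50% keeps 1 − 0.50 × 0.25 = 87.5%. A constant effect is only diluted by this, and with no effect there is nothing for the misclassification to create.

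**4. Would re-cutting on the first session be better?** Take a participant due to start on day 5. Over the 21 placements the first session falls on day 5, 6 or 7 in 15, 5 and 1 cases.

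- *Effect on every day from day 5, rest days included.* Fixed windows keep 100%. With the cut at the first session, a day-6 session puts one program day among five baseline days (1 − 1/5 = 0.8), and a day-7 session puts two among six (1 − 2/6 = 0.667). The average is (15 × 1 + 5 × 0.8 + 1 × 0.667) / 21 = 93.7%.
- *No effect before the first session, then a constant effect.* The first-session cut keeps 100%. Fixed windows keep (15 × 1 + 5 × 0.75 + 1 × 0.5) / 21 = 91.7%.
- *Effect on session days only.* The first-session cut always opens on a session day. Its session density is (15 × 0.75 + 5 × 0.867 + 1 × 1) / 21 = 0.790, against 5/7 = 0.714 for fixed windows. The ratio is 111%, so the change is overstated relative to a typical program day.

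The ranking reverses between the first two cases, and the third inflates the result. The documents do not say which case is closest to the truth.

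**5. What re-cutting cannot recover.** With eight days of wear, a day-6 start leaves three recorded program days and a day-7 start leaves two. With independent days of equal variance, the within-person standard error relative to a 4/4 split is √[(1/n₁ + 1/n₂) / 0.5], which is 1.033 for 5 and 3 days and 1.155 for 6 and 2.

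No power figures are given, because the documents state no effect size, standard deviation or power target for this outcome.

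**The case for a change.** The case for acting is that the protocol's own wording allows a start on another day, with no tolerance, in a program that participants run by themselves at home. The SAP is the operative analysis text and has no rule for such a start. The possible errors also run in different directions: literal day numbers dilute a constant effect, while a cut at the first session can inflate the change. An open choice therefore leaves some room for a decision made after seeing the data, and a sentence in the SAP would close it at almost no cost.

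Much of this stands. Day 1 and initiation are undefined, the dilution arithmetic is right, and a clarifying sentence would do no harm. What does not stand is the step to a needed change. The SAP names each window by its phase as well as its number, so an analyst who finds a program day numbered 4 in the diary has a plain reason not to call it baseline. An incomplete fitting day can be recognised from the monitor's timing data and the form on which removals are recorded. A rule based on a formal program-start date would need a date that neither document says is recorded. The fallback to the first session carries its own bias, as the working shows.

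**Conclusion.** No change to the plan follows. On the intended schedule the protocol and SAP agree exactly. The mismatch is confined to participants who do not start on day 5; the protocol permits such starts, but neither document reports one. For such a participant the literal windows would keep 75% of the contrast at one day off and 50% at two days off, given a constant effect and day 1 as the first wear day. Across the group the loss would be about 6% if a quarter of participants were one day off, and 12.5% if half were; both shares are assumptions.

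This is missing detail that an analyst can fill from the phase labels and the dated diary, and the choice of anchor is a fair trade-off with no clear winner. It touches only the two step-monitor outcomes, which are secondary measures in an uncontrolled pilot of up to 20 people whose SAP calls the study preliminary. The primary outcomes, adherence and the PDQ-39 mobility dimension, are unaffected.
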